8.2.1 Definition of derived variables

Geometric mean will be calculated as:

$$\text{mean}_{\text{geo}} = \exp\left\{\frac{1}{n} \sum_{i=1}^n \ln x_i\right\}.$$

Values that are missing or not available will be ignored in calculation of geometric mean.

CV%_{geo} will be calculated using the following formula:

$$\text{CV}\%_{\text{geo}} = 100\% \cdot \sqrt{\exp V_{\ln} - 1}.$$

Values that are missing or not available will be ignored in calculation of CV%_{geo}.

Absolute change from baseline for a given treatment needs to be calculated, the following formula will be used:

$$\text{Absolute change from baseline} = \text{Post-baseline value} - \text{Pre-dose value}.$$

For weekly scores, Week 0 score is considered to be the baseline value. If Week 0 score is not available, the first non-missing result within 2 weeks of treatment will be used as baseline. For daily scores (e.g. CeD PRO), Day 0 score is considered to be the baseline; in case Day 0 score is not available, the first non-missing result within 2 weeks of treatment will be used as baseline. Otherwise, the given subject will be considered non-evaluable for the specific test. In case pre-dose value doesn't exist (i.e. for biopsy endpoints), screening value will be used as baseline.

In the case where relative (%) change from baseline needs to be calculated, the following formula will be used:

$$\text{Relative (\%) change from baseline} = (\text{Post-baseline value} - \text{Pre-dose value}) / (\text{Pre-dose value}) \cdot 100\%.$$

For weekly scores, Week 0 score is considered to be the baseline value. If Week 0 score is not available, the first non-missing result within 2 weeks of treatment will be used as baseline. For daily scores (e.g. CeD PRO), Day 0 score is considered to be the baseline; in case Day 0 score is not available, the first non-missing result within 2 weeks of treatment will be used as baseline. Otherwise, the given subject will be considered non-evaluable for the specific test. In case pre-dose value doesn't exist (i.e. for biopsy endpoints), screening value will be used as baseline.

Body mass index (BMI) is calculated using the formula:

$$\text{BMI (kg/m}^2\text{)} = \text{weight (kg)} / [\text{height (m)} * \text{height (m)}].$$

Body surface area (BSA) is calculated using Dubois' formula:

$$\text{BSA (m}^2\text{)} = 0.007184 * \text{height (cm)}^{0.725} * \text{weight (kg)}^{0.425}.$$

Table 2 Decimal places for summary statistics of continuous and categorical variables

Statistic	Number of digits
Minimum, maximum	Same as in original data
Mean, median, mean _{geo}	1 more than in original data
SD	2 more than in original data
Frequencies (%)	1 decimal place
CV _{geo}	1 decimal place

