11.2.2 Visit 1 (Week 0/Day 0)

- Review inclusion/exclusion criteria.
- Document visit in the EDC system.
- Allow subject to complete SF-12 v. 2 and EQ-5D.
- Assign e-diary and allow subject to complete the first weekly GSRS and daily CeD PRO.
- Collect vital signs.
- Measure body weight.
- Perform physical examination to include an examination of general appearance; HEENT; lymph nodes; respiratory; cardiovascular; gastrointestinal; musculoskeletal; neurological, psychological and dermatological systems.
- Complete Physician Global Assessment (PGA), BEFORE study drug administration.
- Allow the subject to complete the Patient Global Assessment of Disease (PtGA) BEFORE study drug administration.
- Collect blood and urine for clinical laboratory testing.
- Collect blood sample for PK, ADA and biomarkers BEFORE start of study drug administration. Record date and actual time of sampling.
- Collect Whole Blood for Flow Cytometry.
- Collect blood cell pellet.
- Collect iVYLISA GIP stool sample. The stool sample will be produced within 3 days prior to, or after, the scheduled study visit (± 3 day window).
- Perform urine pregnancy test on FOCBP.
- Administer study medication. See section 18 for administration procedures.

NOTE: Subject should remain in the clinic for a minimum of 1 hour after the end of study drug administration to monitor for new AEs and collect the second PK sample.

- Assess AEs.
- Monitor for changes to concomitant medications.
- Dietitian assessment of the GFD. This assessment can be conducted by phone provided it is conducted within the allotted visit window.
- Collect blood sample for PK 1 hour after END of infusion of study medication. Record date and actual time of infusion beginning, end and sampling.
- Remind subjects to complete the BSFS at each occurrence of a bowel movement and the CeD PRO daily.
- Remind subject to complete the weekly GSRS.
-

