11.2.3 Safety Phone Call (Week 0/Day 1)

- Assess AEs.
- Monitor for changes to concomitant medications.
- Remind subjects to complete the BSFS at each occurrence of a bowel movement and the CeD PRO daily.
- Remind subject to complete the weekly GSRS.

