22.3 MISSING DATA

Subjects withdrawing from study drug administration before Week 6 will be excluded from the PP analysis and the second biopsy will not be collected. Subjects withdrawing on or after Week 6 will be included and the second biopsy will be collected. Missing data after Week 6 will be imputed and the imputation rules will be described in the SAP.

No other data imputation will be done.

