APPENDIX C. BRISTOL STOOL FORM SCALE (BSFS)

APPENDIX D. SAMPLE GASTROINTESTINAL SYMPTOM RATING SCALE (GSRS)

Please read this first:

This survey contains questions about how you have been feeling and what it has been like DURING THE PAST WEEK. Mark the choice that best applies to you and your situation with an "X" in the box

1. Have you been bothered by PAIN OR DISCOMFORT IN YOUR UPPER ABDOMEN OR THE PIT OF YOUR STOMACH during the past week?
 - No discomfort at all
 - Minor discomfort
 - Mild discomfort
 - Moderate discomfort
 - Moderately severe discomfort
 - Severe discomfort
 - Very severe discomfort

2. Have you been bothered by HEARTBURN during the past week? (By heartburn we mean an unpleasant stinging or burning sensation in the chest.)
 - No discomfort at all
 - Minor discomfort
 - Mild discomfort
 - Moderate discomfort
 - Moderately severe discomfort
 - Severe discomfort
 - Very severe discomfort

3. Have you been bothered by ACID REFLUX during the past week? (By acid reflux we mean the sensation of regurgitating small quantities of acid or flow of sour or bitter fluid from the stomach up to the throat.)

- No discomfort at all
- Minor discomfort
- Mild discomfort
- Moderate discomfort
- Moderately severe discomfort
- Severe discomfort
- Very severe discomfort

4. Have you been bothered by HUNGER PAINS in the stomach during the past week? (This hollow feeling in the stomach is associated with the need to eat between meals.)

- No discomfort at all
- Minor discomfort
- Mild discomfort
- Moderate discomfort
- Moderately severe discomfort
- Severe discomfort
- Very severe discomfort

5. Have you been bothered by NAUSEA during the past week? (By nausea we mean a feeling of wanting to throw up or vomit.)

- No discomfort at all
- Minor discomfort
- Mild discomfort
- Moderate discomfort
- Moderately severe discomfort
- Severe discomfort
- Very severe discomfort

6. Have you been bothered by RUMBLING in your stomach during the past week? (Rumbling refers to vibrations or noise in the stomach.)

- No discomfort at all
- Minor discomfort
- Mild discomfort
- Moderate discomfort
- Moderately severe discomfort
- Severe discomfort
- Very severe discomfort

7. Has your stomach felt BLOATED during the past week? (Feeling bloated refers to swelling often associated with a sensation of gas or air in the stomach.)

- No discomfort at all
- Minor discomfort
- Mild discomfort
- Moderate discomfort
- Moderately severe discomfort
- Severe discomfort

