The secondary endpoints Immunological Response 2, VH:CD ratio, Marsh score and total IEL counts will be evaluated by the change from baseline to Week 12 between the AMG 714 dose arm and the placebo arm. BSFS, GSRs and CeD-GSRs will be evaluated by comparing the change from baseline in weekly scores of AMG 714 dose arm and placebo arm.

For the purpose of this study, and in agreement with leading experts in RCD-II (Malamut *et al*, 2010; Nijeboer *et al*, 2015a, 2015b), aberrant IELs will be defined by flow cytometry as surface CD3-negative, intra-cellular CD3-positive IELs (sCD3-, icCD3+). The cut-off chosen for diagnosis of RCD-II is 20% in accordance with most recent studies (Nijeboer *et al*, 2015b). In IHC, these cells are identified as icCD3+, sCD8- and the cut-off is 50% (Nijeboer *et al*, 2015b).

In addition to this standard definition of aberrant IEL (what can be called “classic RCD-II”), it is not uncommon to observe the diagnosis of RCD-II in subjects with an atypical flow cytometric phenotype of the aberrant IELs, yet otherwise meeting the definition of RCD-II. These “Atypical RCD-II” patients may be enrolled in the study and would be part of the intent-to-treat (ITT) population as well as of the per protocol (PP) population except for the analysis of Immunological Response 1 and 2 (since the aberrant cells object of Immunological Response endpoints are different). In other words, all endpoints except Immunological Response 1 and 2 will be assessed with inclusion of any atypical subject enrolled. However, because it is possible that these patients behave differently, sensitivity analyses may also be conducted excluding the atypical subjects.

The **secondary objective** of the study is:

- To assess the safety and tolerability of AMG 714 when administered to adult patients with RCD-II.

The **safety endpoints** of the study are:

- Adverse events (AEs);
- Clinical laboratory tests;
- Physical examination;
- Vital signs;
- Immunogenicity.

Clinical laboratory tests -including immunogenicity-, physical examinations and vital signs will be tabulated by time point and treatment group and reviewed for potential safety signals. All adverse events (AEs) and serious adverse events (SAEs) will be listed and tabulated by system organ class (SOC), preferred term (PT) and further by severity and relatedness to the study drug.

The **exploratory objectives** of the study are:

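### A missing Week 0 or Day 0 diary score is replaced as baseline by a value from the dosing period, and the weekly CeD PRO model averages Week 0 into its pooled treatment contrast

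*SAP*

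**What the plan says.** SAP 2 states that BSFS, GSRS and CeD-GSRS "will be evaluated by comparing the change from baseline in weekly scores". SAP 8.2.1 defines absolute and relative change as the post-baseline value against the pre-dose value. Week 0 is the baseline for weekly scores and Day 0 for daily scores, with CeD PRO named as a daily score. The fallback for weekly scores reads: "If Week 0 score is not available, the first non-missing result within 2 weeks of treatment will be used as baseline". Daily scores have the same fallback when Day 0 is missing. Only if that also fails does the next rule apply: "Otherwise, the given subject will be considered non-evaluable for the specific test".

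Protocol 11.2.2 places the first diary entries at Visit 1, the day of the first infusion: "Assign e-diary and allow subject to complete the first weekly GSRS and daily CeD PRO". For the physician assessment the same list specifies the order: "Complete Physician Global Assessment (PGA), BEFORE study drug administration". The patient global assessment has the same instruction; the diary does not.

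Protocol 22.3 provides for imputation of data missing after Week 6 and then says: "No other data imputation will be done".

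SAP 8.7.6 models the CeD PRO total score, not its change. The daily model runs over Days 0 to 112 and the weekly model over Weeks 0 to 16. Both have a baseline covariate, and the weekly code prints an arm contrast for Week 0.

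**The concern.** No diary record exists before Visit 1, so a substitute baseline is taken after dosing has started. The second infusion is on Day 7 and the third on Day 14, so it may follow more than one infusion. The GSRS looks back over a week ("This survey contains questions about how you have been feeling and what it has been like DURING THE PAST WEEK"), so a Week 1 score used as baseline describes treated time. Any drug effect already present is then subtracted from, or adjusted out of, every later comparison for that subject.

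Where change is the outcome (GSRS, CeD-GSRS and the descriptive CeD PRO tables), a source time point that is kept has a change of exactly zero, and the SAP does not say to drop it. In the CeD PRO models the substitute enters only as the covariate.

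The Week 0 outcome is a separate matter and needs no missing data. If Week 0 is the baseline, or is Day 0 alone, its expected arm difference is zero. The pooled treatment contrast over all 17 weeks includes it.

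At stake is the size of the reported symptom effect on secondary and exploratory endpoints with 16 and 8 subjects planned per arm. The biopsy endpoints use the screening value as baseline, and the Go rule in Protocol 13.1 rests on the two Immunological Responses.

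**Working it through.** The documents give no figure for the diary endpoints, so there is none to reproduce. The planned sample size of 24 does not depend on this rule.

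**Inputs.** From the documents: 16 AMG 714 and 8 placebo subjects; Weeks 0 to 16; Days 0 to 112; one-week GSRS recall. Assumptions: the number *m* of AMG 714 subjects with a substitute (1 to 4); a drug effect growing as E(t) = 1 − exp(−t/τ), with t in weeks and τ = 2, 4 or 8; a baseline slope of 0.8 (range 0.6 to 1.0).

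**1. Source time point kept, change as outcome.** If the affected subjects are otherwise average, the arm's raw Week 1 mean change shrinks by m/16. That is 1/16 = 6%, 2/16 = 13% and 4/16 = 25%. One placebo subject of 8 gives 13%.

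**2. Week 12, Week 1 GSRS substitute.** Averaged over its recall week, the effect at week k is G(k) = 1 − τ[exp(−(k−1)/τ) − exp(−k/τ)]. The share of the Week 12 effect already in the substitute is f = G(1)/G(12). The arm-level loss is (m/16) × slope × f. With baseline as a covariate, analysing change or score gives the same treatment contrast, so this form serves both kinds of model. At slope 0.8:

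| τ (weeks) | G(1) | G(12) | f | loss, m = 1 | loss, m = 4 |
|---|---|---|---|---|---|
| 2 | 0.213 | 0.997 | 21.4% | 1.07% | 4.27% |
| 4 | 0.115 | 0.943 | 12.2% | 0.61% | 2.44% |
| 8 | 0.060 | 0.762 | 7.9% | 0.39% | 1.57% |

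Over slopes 0.6 to 1.0 the range is 0.30% (m = 1, τ = 8, slope 0.6) to 5.34% (m = 4, τ = 2, slope 1.0). A simulated ANCOVA (16 against 8, m = 4, τ = 2, slope 0.8) returned 0.956 of the true effect; the formula gives 1 − 0.0427 = 0.957.

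**3. Week 12, Day 1 CeD PRO substitute.** Here f = E(1/7)/E(12).
- τ = 2: 0.0689/0.9975 = 6.9%
- τ = 4: 0.0351/0.9502 = 3.7%
- τ = 8: 0.0177/0.7769 = 2.3%

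At slope 0.8 the loss is 0.11 to 0.35% for m = 1 and 0.46 to 1.38% for m = 4.

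**4. Direction.** If placebo subjects improve early and one of the 8 has the substitute, that arm's measured improvement falls by about slope × (early improvement)/8. The arm difference then widens. Dilution is the usual direction but not the only one.

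**5. Week 0 as outcome.** With an effect d averaged over Weeks 1 to 16 and zero expected at Week 0, the pooled contrast is (0 + 16d)/17 = 0.941d, a loss of 5.9%. A simulated weekly model (16 against 8, 17 weeks, AR(1) correlation 0.7, constant effect, Week 0 as both outcome and covariate) gave 0.941. The separate Week 1 to Week 16 contrasts do not average Week 0 in.

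**6. Diary weeks.** Days 0 to 112 are 113 days, and 17 full weeks would need 119. Taking Week 0 as Day 0 and Week k as Days 7k−6 to 7k gives 1 + 16 × 7 = 113, an exact fit.

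**The case against.** The first GSRS and CeD PRO entries are made in clinic at Visit 1 and are listed ahead of the blood draws and dosing, so a missing baseline should be rare. No missing rate is given, and 1 to 4 of 16 is an assumption. A CeD PRO substitute could be as early as Day 1, where the loss is small. A GSRS completed one to three days late would still describe mostly pre-dose time. All of this stands, and it is why the effect is given as a small range.

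It can also be said that 8.2.1 is a definition of baseline, not an imputation rule, and that Protocol 22 leaves missing-data detail to the SAP. A reader might infer a plain breach of Protocol 22.3. The documents do not go that far, since 22.3 is mainly about withdrawals and the second biopsy. In substance, though, the rule fills an early missing value with a later one, and the general delegation does not lift the limit in 22.3. The conflict with the SAP's own pre-dose definition does not depend on this argument.

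A reader might also infer that undefined diary weeks bias the arm comparisons. The printed BSFS count model has a log link, a week effect and no baseline term. A short week common to both arms is absorbed there and leaves the arm ratio unchanged. Part of the BSFS text and the SAP appendices are not visible, so a definition there cannot be excluded.

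Finally, the 5.9% concerns one pooled contrast of an exploratory instrument that the SAP says is not validated in RCD-II. That also stands.

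**Conclusion.** The point holds for secondary and exploratory diary endpoints only. The fallback contradicts the SAP's definition of change and is hard to square with Protocol 22.3. Its Week 12 cost is about 0.3 to 5% for 1 to 4 of 16 AMG 714 subjects with a Week 1 GSRS substitute, and about 0.1 to 1.4% (slope 0.8) for a Day 1 CeD PRO substitute. Both ranges rest on the assumed onset, slope and counts, and the direction is usually but not always dilution.

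The 5.9% loss in the pooled weekly CeD PRO contrast needs no missing data. It does require that the covariate is the Week 0 score or that Week 0 is Day 0 alone.

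A reader might go further and say that every subject's weekly CeD PRO baseline is contaminated, with a loss of 5 to 15% at slope 0.8. That requires Week 0 to mean Days 0 to 6 and the baseline to be that week's mean. The documents state neither. Table 1 pairs Week 0 with Day 0, and the reading that fits the day count exactly gives a loss of 0%. The day ranges are a missing detail to supply, not a demonstrated bias. The primary endpoint and the Go decision are untouched.

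**What to change.** In SAP 8.2.1, write: *Baseline for GSRS, CeD-GSRS and CeD PRO is the Visit 1 (Day 0) entry. Values from later days are not used as baseline in the main analysis.*

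- Keep Day 0 entries made after the infusion, but flag them from the diary time stamp. Limiting baseline to pre-infusion entries could discard valid data, because Protocol Appendix K asks for the CeD PRO every evening while Protocol 11.2.2 has the first entry made at the visit. Reconcile those two sections.
- Report the two-week substitution only as a sensitivity analysis, with affected subjects counted by arm and the source time point dropped as an outcome.
- In the main analysis, apply the SAP's existing non-evaluable rule to subjects without a Day 0 entry. A model that retains them is optional.
- In SAP 8.7.6, start the CeD PRO outcome at Day 1 and Week 1, remove the Week 0 arm contrast, and use the Day 0 entry as baseline in both models.
- As a supporting clarification, state the diary weeks, for example Week 0 = Day 0 and Week k = Days 7k−6 to 7k. The phone-call label in Protocol 11.2.3 puts Day 1 in Week 0, so note the departure. Do not report BSFS diarrhoea or constipation percentages for a one-day week; the constipation definition needs at least 3 days.

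The cost is SAP wording and a changed baseline term in three diary analyses, with no new data or patients. The downsides are that a subject without a Day 0 entry leaves that main analysis, and that a one-day CeD PRO baseline is noisier than a weekly mean.

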8.2.2 Missing values

If a discontinuation occurs on or after Week 6 and the second biopsy is collected then the subject is considered evaluable, the results of the second biopsy (pre-maturely done before Week 12) will be used to investigate the change from baseline to Week 12, i.e. the values of parameters obtained from this biopsy will be carried forward for Week 12 efficacy assessments (LOCF). This LOCF will only be done for PP population and only for variables depending on the biopsy.

AMG 714 concentrations below the lower limit of quantification (LLOQ) will be assigned a value of 0.5 x LLOQ in mean calculations for the summary of AMG 714 concentrations. A similar rule will be used for any other assay results below the LLOQ. All assay results over the upper limit of quantification (ULOQ) will be assigned a value of ULOQ.

8.2.3 Handling of data from discontinued subjects

Subjects who are randomized but discontinue before receiving study treatment will not be included in any efficacy or safety analysis, but will be included in the disposition of subjects table. Subjects who receive at least one dose of study treatment will be included in ITT analysis population.

Subjects discontinuing from study drug administration before Week 6 will be excluded from the PP analysis population and the second biopsy will not be collected. Subjects discontinuing on or after Week 6 will be included in the PP analysis population sets if the second biopsy can be collected (in case a subject is lost to follow-up on or after Week 6 and a biopsy cannot be collected, the subject is considered non-evaluable and excluded from the PP population).

Subjects will be considered study completers at Visit 8 (Week 12/Day 84), regardless of whether or not the Final Study Visit (Visit 9; Week 16/Day 112) is attended.

8.3 Disposition of subjects

The number of subjects screened, randomized, completed, or discontinued from the study and the reason for study discontinuation will be tabulated by treatment group and site as appropriate. Subject count by analysis population will also be tabulated. Major protocol deviations will be summarized by treatment group.

Disposition of subjects, informed consent signing information, and inclusion/exclusion criteria will also be listed by subject.

8.4 Demographic and baseline characteristics

Demographic and baseline characteristics collected and presented for this study, include: age, sex, race, ethnicity, weight, height, BMI, BSA, urine drug and alcohol screen, 12-lead ECG, medical history, and primary diagnosis (including celiac serology history). Compliance to pre-screening fasting will also be investigated.

Demographic and baseline characteristics are assessed at screening. Weight is additionally measured throughout the study at time points specified in [Appendix 1](#) and BMI is calculated based on these weight measurements and screening heights.

Demographic and baseline characteristic will be presented by summary statistics and tabulated by treatment group, as well as listed. Medical history will be additionally broken down by system organ class (SOC) and preferred term (PT). 12-lead ECG, primary diagnosis, urine drug and alcohol screen and fasting compliance will only be listed.

Both ITT and PP populations will be used for the analysis of demographic and baseline characteristics.

8.5 Extent of exposure and compliance

Extent of exposure will be summarized showing:

- Number of subjects exposed to placebo or AMG 714 at each visit.

Extent of exposure will be tabulated by treatment group and visit using the ITT analysis population. Total exposure and number of doses will also be listed cumulatively for all subjects. Start and end dates and times of IV infusions along with duration of infusion will only be listed.

8.6 Analysis of efficacy

8.6.1 Primary efficacy variable

Primary efficacy endpoint of the study is:

- Immunological Response 1: Relative (%) change from baseline to Week 12 in the % of aberrant intestinal intraepithelial lymphocytes (IELs) vs total IELs as assessed by flow-cytometry.

The primary endpoint will be analysed using analysis of covariance (ANCOVA), where the baseline % aberrant IELs vs total IELs will be included as a covariate and treatment group as a fixed effect in the statistical model.

The analysis of the primary endpoint will be carried out using the PP population. Subjects having Week 6 biopsy data who are lost to follow-up for further visits will have their Week 6 value carried forward for the final analysis (more details available in *Chapter 8.2.2 Missing values*).

The following model will be fitted:

$$Y_{ij} = \mu + \beta \cdot \text{baseline \% IEL vs total IEL}_{ij} + \alpha_j + \varepsilon_{ij},$$

where

Y_{ij} is the relative (%) change from baseline in the % of aberrant IELs vs total IELs for subject i ($i = 1, \dots, n_j$) from treatment group j ($j = 1, 2$),

μ is the overall mean,

β is the parameter estimate of baseline % IELs vs total IELs,

α_j is the fixed effect due to treatment j ,

ε_{ij} is the random error for subject i from treatment group j ; $\varepsilon_{ij} \sim N(0, \sigma_\varepsilon^2)$.

The following SAS code will be used to fit the above-specified model (NOTE: SAS codes provided in this document may be modified based on statistical considerations, without requiring SAP amendment):

```
proc glm data=IELt alpha=0.1 outstat=F_tests;
  class trt;
  model IELt_change = bl_IELt trt / clparm solution SS1 SS2;
  estimate "AMG 714 vs Placebo" trt 1 -1;
  lsmeans trt /cl stderr alpha=0.05;
  ods output ParameterEstimates=Par_est LSMeanCL=LS_meanCL
             LSMeans=LS_mean OverallANOVA=ANOVA Estimates=Eff_est;
run;
```

The modelling results (ANOVA table, parameter estimates, estimated treatment effect, marginal (i.e. least squares) means estimates and results of the check of assumptions) will be tabulated and 90% confidence intervals added, where appropriate.

As a secondary assessment, the same model will be fitted using the absolute change in % of aberrant IELs vs total IELs as a response variable. The modelling results (ANOVA table, parameter estimates, estimated treatment effect, marginal (i.e. least squares) means estimates and results of the check of assumptions) will be tabulated and 90% confidence intervals added, where appropriate.

A frequency table by treatment group will be used to summarize the percentage of patients who reach normalization of aberrant IEL counts by flow cytometry measured as aberrant IELs < 20% of total IEL based on the second biopsy after Week 6. Additionally, a frequency table of subjects with at least 20% reduction from baseline in the % aberrant IELs vs total IELs by treatment arm will also be created, if applicable.

The baseline and post-baseline values along with the change from baseline values (both relative and absolute) will also be described by summary statistics and tabulated by treatment group. Baseline and post baseline values will also be listed.

